7.2 Temporary Discontinuation of Study Intervention

Brief temporary discontinuation of study intervention is permitted during the study, providing inhalation of study intervention is completed within 20 minutes.

Study intervention should be temporarily discontinued in the following circumstance:

1. Clinical intolerance to nebulization.

An individual administration of study treatment will be stopped, and supplemental oxygen if applicable resumed, if threshold limits of SpO₂ 89% or heart rate 120 beats/min (or as indicated by the Investigator) are exceeded (see Sections 4.2 and 8.1.2).

The participant may continue with subsequent doses if the Investigator judges that the benefit / risk ratio remains positive. In this case, the instruction to continue should be duly recorded in the participant's hospital file and the subsequent nebulization should be closely monitored.

Refer to Section 6.1 for information on staggered dosing in the first 10 participants.

7.3 Participant Discontinuation/Withdrawal from the Study

A participant may withdraw from the study at any time at his/her own request or may be withdrawn at any time at the discretion of the Investigator for safety, behavioral, or administrative reasons. The participant will be definitively discontinued from both the study intervention and from the study at that time.

If the participant withdraws consent for disclosure of future information, the Sponsor may retain and continue to use any data collected before such a withdrawal of consent.

If a participant withdraws from the study, he/she may request destruction of any samples taken and not tested, and the Investigator must document this in the site study records.

At the time of discontinuing from the study, if possible, an early discontinuation assessment should be conducted, as shown in the SoA (Table 1-1).

7.4 Loss of Participants to Follow-Up

A participant will be considered lost to follow-up if he or she is unable to be contacted by the study site. The following actions must be taken if a participant cannot be contacted at Day 14 or Day 28:

- The site must attempt to contact the participant and counsel the participant on the importance of maintaining the assigned schedule and ascertain whether or not the participant wishes to and/or should continue in the study.
- In cases in which the participant is deemed lost to follow-up, the Investigator or designee must make every effort to regain contact with the participant (where possible,

three telephone calls and, if necessary, a certified letter to the participant's last known mailing address or local equivalent methods). These contact attempts should be documented in the participant's medical record/CRF.

- Should the participant continue to be unreachable, he/she will be considered to have withdrawn from the study.

8 Study Assessments and Procedures

Study procedures and their timing are summarized in the SoA (Table 1-1). Protocol waivers or exemptions are not allowed.

Immediate safety concerns should be discussed with the Sponsor immediately upon occurrence or awareness to determine if the participant should continue or discontinue study intervention.

Adherence to the study design requirements, including those specified in the SoA, is essential and required for study conduct.

All screening evaluations must be completed and reviewed to confirm that potential participants meet all eligibility criteria. The Investigator will maintain a screening log to record details of all participants screened and to confirm eligibility or record reasons for screening failure, as applicable.

Procedures conducted as part of the participant's routine clinical management (e.g., blood count) and obtained before signing of the ICF may be utilized for screening or baseline purposes provided the procedures met the protocol-specified criteria and were performed within the time frame defined in the SoA (Table 1-1).

The maximum amount of blood collected from each participant, should be approximately 20 mL per occasion (Screen, Day 1, Day 3, Day 7, Day 10 and Day 28).

Repeat or unscheduled samples may be taken for safety reasons or for technical issues with the samples.

Informed Consent

Informed consent must be documented according to Appendix 1, Section 10.1.3.

Eligibility Criteria

All inclusion and exclusion criteria will be reviewed by the Investigator or designee to ensure that the participant qualifies for the study.

Participant Identification Card

All participants will be given a participant identification card identifying them as participants in a research study. The card will contain study site contact information (including direct telephone numbers) to be used in the event of an emergency. The Investigator or qualified designee will provide the participant with a participant identification card immediately after the participant provides written informed consent. At the time of intervention allocation/randomization, site personnel will add the intervention/randomization number to the participant identification card.

Medical History

A medical history will be obtained by the Investigator or qualified designee. The medical history will collect all active conditions and any condition diagnosed that the Investigator considers to be clinically relevant. Details regarding the disease for which the participant has enrolled in this study will be recorded separately and not listed as medical history.

Prior and Concomitant Medications Review

The Investigator or qualified designee will review prior medication use and record prior medications taken by the participant within 3 months prior to screening. This should include a history of hypertension medication, in particular angiotensin-converting enzyme inhibitors and angiotensin receptor blockers.

The Investigator or qualified designee will record medication, if any, taken by the participant during the study through the last assessment. Concomitant medications will be recorded on an ongoing basis during the study (or longer if related to an SAE).

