Study intervention, TID ⁶		X	X	X				A staggered dosing approach will be used for the first 10 participants (up to the first IDMC safety review). Each RESP301 dose will be administered by intermittent inhalation to monitor the tolerability and response to RESP301 (see Sections 6.1 and 9.6). Where possible study intervention should be administered at approximately the same times each day At least 6 hours between 2 consecutive doses
AE/SAE review	X	X	X	X	X	X	X	
Concomitant medication review	X	X	X	X	X	X	X	
Pre Treatment oxygen / respiratory assessment ⁷	X	X	X	X				
SpO ₂ on room air (after at least 1 minute) prior to study intervention administration and immediately at the end of nebulization ⁶		X	X	X				See Section 8.1.2

Procedure	Screening (up to 48 hours before Day 1 ¹)	Intervention Period			Early withdrawal	Efficacy follow-up (Day 14) ² (± 2 days)	EoS efficacy and safety follow-up (Day 28) ² (± 2 days)	Notes
		Day 1 ¹	Daily while hospitalized	Day 10 / hospital discharge				
Modified WHO ordinal scale	X	X	X	X		X	X	See Section 8.1.1
NEWS 2 assessment ⁷		X	X	X				Prior to study intervention in the morning. See Section 8.1.3

Abbreviations: AE=adverse event; aPTT= activated partial thromboplastin time; CBC=complete blood count; Chem 7=blood chemistry panel (sodium, potassium, chloride, bicarbonate/CO₂, blood urea nitrogen, creatinine, glucose); CV=cardiovascular; ECG=electrocardiogram; IDMC=Independent Data Monitoring Committee; LFTs=liver function tests; mHb=methemoglobin; PT/INR=prothrombin time/international normalized ratio; RT-PCR=reverse transcription-polymerase chain reaction; SAE=serious adverse event; TID=three times daily.

1. Screening and randomization may be on the same day, providing all eligibility criteria are met.
2. For participants who are already discharged at either the Day 14 or Day 28 (EoS) follow-up, there will be a phone call to check AEs/SAEs, concomitant medications, and modified WHO ordinal scale. At EoS, safety laboratory tests (nitrite and mHb only) and weight will be collected for participants in hospital only.
3. COVID-19 infection must be confirmed and documented in chart with a positive result on a validated test.
4. At Screening: CBC, chem 7, mHb, LFTs, and coagulation (PT/INR, aPTT).
On Day 1, Day 3, Day 7 and Day 10, or early withdrawal: CBC, chem 7 (per SOC), and mHb.
On Day 28: nitrite and mHb (participants in hospital at EoS only).

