- Experiences an event that requires permanent discontinuation as described in Section 7.1.

In the above cases, participants will be considered as ongoing in the study until the final Safety follow-up phone call (Day 28). Participants will be withdrawn from the study prior to Day 10 (Early withdrawal) only if they withdraw consent.

The total study duration for a participant from screening to last follow up will be up to 30 days (± 2 days).

Participants will be stratified by country and presence of risk factor(s) for severe outcomes of COVID-19, based on comorbidities and age, as detailed in Section 6.3.

Two interim analyses are planned (see Section 9.5 for details).

An IDMC will be responsible for closely reviewing the safety and efficacy data from the interim analyses and for providing their recommendations on continuation of the study. The IDMC will meet after 10, 20, 60 and 150 participants have completed the study (see Sections 9.5 and 9.6).

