9.4.1 General Considerations

All statistical analyses will be conducted using SAS, Version 9.4 or later. Baseline characteristics will be summarized by treatment arm. For continuous measures the mean and standard deviation (SD) will be summarized. Categorical variables will be described by the proportion in each category. In addition, 95% confidence intervals (CIs) will be computed as indicated.

All the categorical variables including the primary endpoint will be summarized by treatment with the numbers and percentages of the participants. Treatment difference will be tested using a Cochran–Mantel–Haenszel test stratified by 1) country and 2) participant's clinical status at Baseline. For the categorical endpoints, relative risk and its 95% CI will be presented.

All of the continuous variables, including the changes from Baseline, will be summarized by treatment with the means, SD, medians and the ranges. The mixed model with repeated measurements /analysis of covariance model with treatment, country, participant's clinical status at Baseline and visit as the model term, and Baseline value as the covariate will be used to test for the significance of the treatment difference. Least square means, standard errors, 95% CIs and p-values will be presented.

Time to event endpoints will be analyzed using the Cox Proportional Hazard model with treatment, participant's clinical status at Baseline and country as the model term. The hazard ratio of RESP301+SOC versus SOC will be presented along with 95% CI and p-value from the model. The Kaplan-Meier curves of the time to events will be presented by treatment for each applicable endpoint.

Handling of missing data

If participants are discharged from the hospital prior to Day 14 due to improvement of the clinical status and their status on Day 14 cannot be obtained, their status on Day 14 for the primary endpoint will be imputed with the status on the day of discharge. Depending on the reasons for missing data on the primary endpoint up to Day 14, additional sensitivity analyses will be performed. Further details on handling on missing data will be provided in the SAP.

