9.4.2 Primary Endpoint

The primary endpoint is the proportion of participants who progress by at least one level higher on the modified WHO ordinal scale by Day 14.

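### Section 7.4 deems a participant who stays unreachable at Day 14 withdrawn from the study, and nothing in the protocol secures that person's Day 28 contact or vital status

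*Protocol*

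**What the plan says.** All references are to the current protocol text, which admits WHO levels 3 and 4.

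- **Trigger.** Section 7.4: "The following actions must be taken if a participant cannot be contacted at Day 14 or Day 28". Repeated attempts follow (three telephone calls where possible and, if needed, a certified letter), and these must be documented in the medical record or CRF.
- **Outcome of failed attempts.** Section 7.4: "Should the participant continue to be unreachable, he/she will be considered to have withdrawn from the study".
- **Effect of withdrawal.** Section 7.3: "The participant will be definitively discontinued from both the study intervention and from the study at that time".
- **Withdrawal in the design section.** Section 4.1: "Participants will be withdrawn from the study prior to Day 10 (Early withdrawal) only if they withdraw consent". It sets no such limit after Day 10, which is when Section 7.4 operates.
- **Follow-up calls.** For participants already discharged at Day 14 or Day 28, footnote 2 of the Schedule of Activities says "there will be a phone call to check AEs/SAEs, concomitant medications, and modified WHO ordinal scale".
- **Primary endpoint.** Section 9.4.2: "The primary endpoint is the proportion of participants who progress by at least one level higher on the modified WHO ordinal scale by Day 14". Mortality by Day 28 is an additional secondary endpoint (Section 9.4.3).
- **Missing data.** Section 9.4.1 imputes discharge status when a participant discharged before Day 14 with improvement has no obtainable Day 14 status. It adds: "Depending on the reasons for missing data on the primary endpoint up to Day 14, additional sensitivity analyses will be performed".

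**The concern.** Once a participant has gone home, the protocol schedules only two further contacts, at Day 14 and Day 28. If the first fails, the second is the only remaining scheduled source of information on what happened after discharge. Section 7.4 changes that person's status to withdrawn before the second contact falls due, and Section 7.3 attaches the end of participation to that status. A site following the text has no instruction to make the Day 28 call.

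Two things are at stake. Vital status at Day 28 may go unrecorded for people who could have been found. And a favourable value may be imputed for the primary endpoint where an observation was obtainable. The trial is open-label, so neither the chance of losing contact nor the chance of an unseen progression need be equal between arms. A later analysis plan can choose how to treat missing values, but it cannot supply data that sites were not told to collect.

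**Working it through.** **1. Does any text secure the Day 28 contact?**

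- Section 9.3 (ITT definition) and Appendix 5 (10.5.1, item 1) promise follow-up for the primary endpoint to those who withdraw from treatment. A participant deemed withdrawn from the study is outside both.
- Section 4.1 keeps participants who permanently discontinue treatment in the study to Day 28. It does not address loss of contact.
- Section 8.3.1 does not oblige investigators to look for adverse events once participation has ended.
- Section 10.4.4 requires serious adverse events up to 18 days after the last dose to be reported, but it creates no duty to seek them, and SOC participants have no last dose.
- Timing: Day 14 ± 2 is Day 12 to 16 and Day 28 ± 2 is Day 26 to 30, so the contacts are 26 − 16 = 10 to 30 − 12 = 18 days apart. That is long enough to exhaust the listed attempts before Day 28.

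None of these passages secures the call.

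**2. Which outcomes could be misclassified?**

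A living discharged participant is at level 1 or 2 (Section 8.1.1), below either entry level, so imputing discharge status scores no progression. That is wrong only for these events by Day 14:

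| Entry level | Wrongly scored as not progressed | Correctly scored |
|---|---|---|
| 3 | Death; readmission at level 4 or above | Readmission at level 3 |
| 4 | Death; readmission at level 5 or above | Readmission at level 3 or 4 |

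In-hospital progression is already captured by daily scoring. The Day 28 call as described records the level at that time, not the worst level up to Day 14. It could reveal a death or readmission, but scoring Day 14 from it needs added questions.

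**3. How many?**

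The protocol gives no discharge rate, missed-call rate or Day 28 answer rate. As an illustration, assume 60-80% of 300 are discharged before Day 14, 5-10% of those miss the Day 14 calls, and half of those would answer at Day 28.

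- Missed at Day 14: 300 × 0.60 × 0.05 = 9 to 300 × 0.80 × 0.10 = 24.
- Reachable at Day 28: half of these, 4.5 to 12.

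Only the second line can be put down to the rule. Within it, only participants who had an event from the table would have a wrong primary outcome, and nothing in the protocol sizes that group.

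**4. Effect on power.**

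Inputs (Sections 9.2 and 9.5): 30% vs 15%, 100 SOC and 200 RESP301+SOC, final one-sided alpha 0.0249.

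The stated 300 is reproduced to within 3% by the continuity-corrected two-proportion formula: 291 at alpha 0.025 and 294 at 0.0249. Without the correction the formula gives 264.

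Uncorrected power at 300 is Φ[(p1 − p2 − z·se0)/se1]:

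- pooled rate = (30 + 30)/300 = 0.20
- se0 = √(0.20 × 0.80 × (1/100 + 1/200)) = 0.0490
- se1 = √(0.21/100 + 0.1275/200) = 0.0523
- z = 1.962
- power = Φ[(0.15 − 0.0961)/0.0523] = Φ(1.03) = 84.9% (81.2% with continuity correction)

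With an assumed loss L at Day 14, either the lost are left out (arm sizes × (1 − L)) or they are counted as not progressed at equal risk (rates × (1 − L)):

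| L | Left out | Counted as not progressed |
|---|---|---|
| 0% | 84.9% | 84.9% |
| 2% | 84.2% | 84.0% |
| 5% | 83.1% | 82.6% |
| 10% | 81.1% | 80.1% |
| 15% | 79.0% | 77.4% |

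The last column gives lost participants the full 30% or 15% risk. Participants discharged after improvement have already had their in-hospital course recorded, so it leans towards overstating the loss.

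**The case against.** The strongest reply is that the text never cancels the Day 28 call. Section 7.4 sets no date by which someone counts as persistently unreachable, so attempts begun at Day 14 may still be open at Day 28. The Schedule of Activities does not make the Day 28 call conditional on a completed Day 14 call. Section 7.4 does not cite Section 7.3, whose sentence on discontinuation follows one about withdrawal by the participant or the investigator. This stands as far as it goes. A reader might infer that the Day 28 call is never made, and the documents do not support that. They support only that it is not secured.

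Three other strong readings also fail:

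- **That the reason for missingness is erased.** The attempts must be documented, and Section 8.3.3 treats loss to follow-up as its own end state. The disposition status blurs the reason but need not remove it. Coding detail may sit in the CRF or the SAP, which was not available.
- **That every readmission after discharge counts as a success wrongly.** Only death or readmission above entry level does.
- **That every participant lost at Day 14 loses Day 28 vital status through the rule.** Those who would not have answered at Day 28 are missing under any wording.

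It is also fair to say that the favourable imputation comes from Section 9.4.1 rather than Section 7.4. The two act together, however. Section 7.4 affects whether an observation is sought, and Section 9.4.1 fills the gap if it is not. Appendix 5 (10.5.1, item 1) itself records that the meaning of this imputation is unsettled.

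**Conclusion.** The point holds as a gap in the follow-up rule. A participant still unreachable after a failed Day 14 contact is classed as withdrawn from the study, and no text secures the Day 28 contact or a vital-status check. Day 28 mortality is the clearest loss. The primary endpoint is affected only for participants discharged with improvement who then died, or were readmitted above entry level, by Day 14, and whom the Day 28 call would have found.

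The protocol gives no basis for counting them; the 4.5 to 12 reachable participants rest wholly on the assumptions stated. Power is not the issue: at an assumed 5-10% loss it stays between 80.1% and 83.1%, against 84.9% with none. The open question is bias if loss or unseen progression differs between open-label arms, and no figure in the protocol sizes that. This is a cheap improvement worth making, not a flaw that undermines the design.

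**What to change.** Change the last bullet of Section 7.4:

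- A participant unreachable at Day 14 stays in the study, and the Day 28 contact is still attempted unless consent has been withdrawn.
- That call also records any death, readmission and highest oxygen or ventilation support since discharge, with dates, so that progression by Day 14 can be scored.
- Loss to follow-up is declared only after the Day 28 attempts fail, and is coded separately from withdrawal of consent.

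The cost is a short rewording of Section 7.4 and a few questions in a call that is already scheduled. No new visit is needed. The drawback is some recall error in events and dates reported about two weeks later. For these participants that replaces a favourable imputed value with an imperfect observation.

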8.1 Efficacy Assessments

8.1.1 Modified WHO Ordinal Scale

A modified WHO ordinal scale will be used for consistency with the recent study of lopinavir-ritonavir in adults hospitalized with severe COVID-19 (Cao et al, 2020), to record the participant's status at the time of assessment. The modified WHO ordinal scale includes the following levels:

1. Not hospitalized, no limitations on activities;
2. Not hospitalized, limitation on activities;
3. Hospitalized, not requiring supplemental oxygen;

4. Hospitalized, requiring supplemental oxygen;
5. Hospitalized, on non-invasive ventilation or high-flow oxygen devices;
6. Hospitalized, on invasive mechanical ventilation or extra corporeal membrane oxygenation (ECMO);
7. Death.

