hypoxia at the tissue and cellular level (temperature, pH, tissue blood flow). As a result, there is no consensus about what constitutes normal and abnormal oximetry (ATS/ACCP, 2003). To support and guide the team in charge of study intervention administration, a default value of SpO₂=89% and heart rate (120 beats/min) has been proposed as a suitable limit of tolerance. However, for the reason stated above, this limit can be overruled by the Investigator in either direction.

Newly released guidelines for ongoing clinical trials during the COVID-19 pandemic have emphasized the need to reduce the burden on sites and clinical trial personnel/investigators whether they be administrative, site visit, or other burdens (ACRO, 2020; EMA, 2020; HRS, 2020). Thus, without blinding and a placebo, along with minimal procedures, the additional burden on clinical staff has been reduced as much as possible.

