6.3 Measures to Minimize Bias: Randomization and Blinding

This is an open-label study; however, the specific intervention to be taken by a participant will be assigned using an interactive voice response system (IVRS)/interactive web response system (IWRS). The site will contact the IVRS/IWRS prior to the start of study intervention administration for each participant. The site will record the intervention assignment on the applicable case report form (CRF), if required.

Potential bias will be reduced using a central stratified randomization to assign participants into one of the study treatment arms, RESP301+SOC or SOC (control), with a randomization ratio of 2:1. Participants will be stratified by country and presence of risk factors for severe outcomes of COVID-19, based on comorbidities and age as follows:

1. Age >65 years
2. Ongoing or currently treated diabetes mellitus
3. Ongoing or currently treated hypertension
4. Ongoing or currently treated cardiovascular disease
5. Ongoing or currently treated chronic lung disease
6. Cancer history of less than 3 years, basal cell skin carcinoma excluded
7. Ongoing or currently treated chronic kidney disease

Participants will be stratified as no risk factor (none of the above criteria), one risk factor (one single of the above) or high-risk factor (2 or more of the above).

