6.5 Concomitant Therapy

During the study, participants will receive institutional SOC for the treatment of COVID-19.

Any medication or vaccine (including over-the-counter or prescription medicines, vitamins, and/or herbal supplements) that the participant is receiving at the time of enrollment or receives during the study must be recorded along with:

- Reason for use
- Dates of administration including start and end dates
- Dosage information including dose and frequency and route

The Medical Monitor should be contacted if there are any questions regarding concomitant or prior therapy.

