9.1 Statistical Hypothesis

RESP301 reduces the rate of progression in the modified WHO ordinal scale in COVID-19 (see Section 8.1.1).

The endpoint of worsening level on the WHO ordinal scale represents a composite endpoint of scales above the entry level, being (i) death (level 7), (ii) hospitalized, on invasive mechanical ventilation or ECMO (level 6), (iii) hospitalized, on non-invasive ventilation or high-flow oxygen devices (level 5) , or, for those patients who were recruited at WHO ordinal scale 3, (iv) hospitalized, requiring supplemental oxygen.

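### For level-3 entrants the lowest primary event is starting oxygen, a discretionary step in an open-label trial, and no recorded reading is tied to it

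*Protocol*

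**What the plan says.** The file holds two versions of the protocol. This point concerns the amended one, which admits WHO levels 3 and 4.

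- Section 9.4.2 sets the primary endpoint as the proportion of "participants who progress by at least one level higher on the modified WHO ordinal scale by Day 14".
- Section 9.1 lists the qualifying states as levels 5, 6 and 7 and adds, "for those patients who were recruited at WHO ordinal scale 3, (iv) hospitalized, requiring supplemental oxygen".
- Section 8.1.1 describes level 4 only as "Hospitalized, requiring supplemental oxygen". It gives no SpO2 value, minimum duration, flow or confirmation rule.
- Section 4.2 explains the open-label choice as a way of lightening the load on sites: "Thus, without blinding and a placebo, along with minimal procedures".
- Section 6.5 leaves background care to the hospital: "During the study, participants will receive institutional SOC for the treatment of COVID-19".
- Section 6.3 states how bias is to be limited: "Potential bias will be reduced using a central stratified randomization to assign participants into one of the study treatment arms". No blinded or central review of the ordinal scale is described.

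SpO2, oxygen flow and mode, FiO2 and NEWS 2 are recorded (Schedule of Activities footnote 7; sections 8.1.2 and 8.1.3). None of them is tied to the assignment of level 4.

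**The concern.** When only level-4 patients were eligible, a primary event meant high-flow oxygen, ventilation or death. Admitting level 3 added a lower step. Low-flow oxygen can be started somewhat sooner or later on judgement, and the people judging can know the arm. Central randomization makes the arms comparable at entry. It does nothing to keep the threshold for starting oxygen the same in both arms afterwards.

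A difference in that threshold would enter the primary endpoint directly, and also the secondary endpoint of time to progression. The stratified Cochran-Mantel-Haenszel test in section 9.4.1 adjusts for baseline status. It cannot adjust for how the outcome came about.

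This is a protocol matter because it concerns data capture. If no reading is tied to the start of oxygen, no later analysis can separate a drug effect from a difference in readiness to start it.

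**Working it through.** **The plan's own figure.** Inputs from section 9.2: 30% versus 15%, 2:1, one-sided 0.025, 80% power. The pooled rate is (0.30 + 2 × 0.15)/3 = 0.20.

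Control n = [1.960 × √(0.20 × 0.80 × 1.5) + 0.842 × √(0.21 + 0.1275/2)]² / 0.15² = (0.960 + 0.441)²/0.0225 ≈ 87.2, so 88 per control arm and 264 in total. With a continuity correction this becomes 97 and 291, close to the stated 300. Power at 100 versus 200 is 84.9% uncorrected and 81.3% corrected. The stated N = 300 is reproduced.

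**Effect of a difference in oxygen starts.**
- From the protocol: 100 versus 200 participants, and one-sided 0.0249 at the final analysis (section 9.5), critical value 1.9617.
- Assumed, because the documents give neither: the level-3 share s (30 to 70%) and the between-arm difference d in oxygen starts among level-3 entrants (5 to 10 points).
- Also assumed: no drug effect, a 30% event rate in both arms, no interim looks, an unstratified test, and d favouring RESP301.

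Spurious difference D = s × d, split evenly around 30%. SE = √[pC(1−pC)/100 + pT(1−pT)/200]. Type I error = P(Z > 1.9617 − D/SE).

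Example with s = 50% and d = 10 points: D = 0.05, pC = 0.325, pT = 0.275, SE = 0.0565, D/SE = 0.885, and P(Z > 1.077) = 14.1%.

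| Level-3 share | d | D | One-sided type I error |
|---|---|---|---|
| 30% | 5 | 1.5 points | 4.5% |
| 30% | 10 | 3.0 points | 7.6% |
| 50% | 5 | 2.5 points | 6.5% |
| 50% | 10 | 5.0 points | 14.1% |
| 70% | 5 | 3.5 points | 9.0% |
| 70% | 10 | 7.0 points | 23.4% |

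An exact calculation for the pooled two-proportion test starts from 2.6% with no bias. It gives 6.8% and 14.9% for the two 50% rows.

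**How large d must be (exact calculation).** The error reaches 5% at d = 6.6, 3.3 and 2.2 points for level-3 shares of 25, 50 and 75%. An even chance of a false positive needs d = 43, 22 and 14 points.

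**The other direction.** Suppose the true rates are 30% and 15%, and a 2.5-point artefact runs against RESP301, split evenly: 28.75% versus 16.25%. The pooled rate is 0.2042, the null SE is √(0.2042 × 0.7958 × 0.015) = 0.0494, and the alternative SE is 0.0522. Power = Φ[(0.125 − 1.9617 × 0.0494)/0.0522] ≈ 70%, against 84.9% without the artefact.

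**The case against.** Much of the opposing case stands.

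- A reader might infer that oxygen is the only primary event for level-3 entrants. It is not: section 9.1 also counts levels 5 to 7. Oxygen is the lowest and most discretionary step.
- A reader might infer that knowing the arm is enough to deliver a positive trial. The figures do not support that. They show inflated error, and a false positive becomes more likely than not only with a large difference, about 22 points at a 50% level-3 share.
- The protocol does not say who starts ward oxygen or scores the scale. That unblinded staff do so is inferred from the open-label design and from "participants will receive institutional SOC for the treatment of COVID-19".
- The direction is not settled. Only the active arm has monitored nebulization, with an 89% alarm and oversight afterwards (footnote 6). That could prompt more oxygen there and work against RESP301.
- The remark in section 4.2 that "there is no consensus about what constitutes normal and abnormal oximetry" explains why investigators may override the limit for stopping a nebulization. It is not about starting ward oxygen, and the point does not rest on it.
- The recorded SpO2 and NEWS 2 data allow some cross-checking, and an unseen SAP may add analyses. But the scheduled footnote 7 and NEWS 2 readings end at Day 10 or discharge, are not timed to the start of oxygen, and leave Days 11 to 14 and readmissions uncovered. An SAP cannot supply a reading that was never taken.

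The strongest objection is to changing the primary definition itself. A cut-off chosen mid-trial would bring its own bias risk and would lose events. At N = 300 with a 50% relative reduction, power would be about 76%, 66% or 53% if the control rate fell to 25%, 20% or 15% (assumed rates). Unblinded staff would also decide whether to take the qualifying reading. This is why the primary definition should be kept.

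**Conclusion.** The point holds in a limited form. For level-3 entrants the primary endpoint includes a discretionary, unblinded event that has no objective criterion, and no outcome-scoring safeguard is described. A difference between arms in readiness to start oxygen, in either direction, would be read as treatment effect.

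If it favours RESP301 by 5 to 10 points in level-3 entrants forming 30 to 70% of the trial, one-sided type I error rises from 2.5% to roughly 4.5% to 23%. Share, size and direction are all assumptions. The amendment rationale says only that a significant proportion of admissions were by then grade 3. The documents do not show that such a difference will occur. They show that the trial could not detect it or bound it.

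**What to change.** Keep the primary definition, and do not change when anyone receives oxygen.

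Add one CRF field for the last SpO2 and air/oxygen status before ward oxygen was started. Collect it in the same way in both arms through Day 14, including readmissions. Exclude oxygen given for the nebulization procedure and the footnote 6 readings, which are taken in the active arm only.

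In sections 8.1.1 and 9.4.2, pre-specify before the next interim:

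(a) a sensitivity analysis of the primary endpoint in which a 3-to-4 change counts only if that reading supports it, or if level 5 or above or death follows by Day 14. The sponsor fixes the SpO2 value for scoring without sight of outcome data by arm;

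(b) a sensitivity analysis counting only level 5 or above or death, for all participants;

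(c) separate reporting by arm of 3-to-4 changes without a supporting SpO2.

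The cost is one CRF field, some extra analysis, and lower power in (a) and (b) because fewer events count. Neither should be expected to reach significance on its own. Their use is to show whether the primary result depends on unsupported oxygen starts.
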